4.3.4.2 Handling Missing Severity and Causality Data of AEs

- Handling of unknown severity grades:
 - If the severity of an AE is missing, the severity will be designated as “severe” for analysis purposes.
- Handling of unknown causality assessment data:
 - If the causality of an AE is missing, the causality of the AE will be designated as “related” for analysis purposes.

4.3.4.3 Prior and Concomitant Medications

For prior and concomitant medication, there will be no imputation of missing data. If missing data prevents the medication being classified as prior or concomitant, the medication will be considered as concomitant for the data listings.

4.3.5 Interim Analysis

As participants in each dosing group complete their Week 16 visit, data clean-up and soft-lock will be performed for each cohort, in order to allow an interim assessment of PK, PD and safety data. PK/PD analysts will be permitted access to unblinded data, and to facilitate preparation of blinded data summaries for presentation to the Sponsor. The randomization code will be provided to the bioanalytical laboratories responsible for the analysis PK and PD endpoints. Following analysis of the

PAREXEL International

Statistical Analysis Plan

samples but prior to provision of the data to PAREXEL's statistician, the laboratory will re-code the data back to the corresponding original unique sample ID numbers, enabling differentiation but not identification of the subjects in order to maintain blinding integrity for the other assessments of the clinical study, until after database lock. The full randomization code will be broken only for purposes of data analysis and reporting or safety reasons. This will occur once all final data have been entered into the database and all data queries have been resolved, coding is complete, the assignment of subjects to the analysis sets has been completed and the database has been locked.

Interim summaries of PK, PD and safety data for selected or entire cohorts (inclusive of both VIS649 and placebo recipients, and therefore, still blinded) may be utilized for various reporting purposes prior to full database lock and unblinding if deemed appropriate.

4.3.6 Subject Information

4.3.6.1 Randomization Scheme and Codes

Each subject has their unique enrollment (subject) number and randomization number. The randomization number will be used as subject identification in TLFs.

4.3.6.2 Subject Disposition

The completion status and the reason for discontinuation of subjects using the randomized population will be listed [Listing 16.2.1.1] and summarized [Table 14.1.1]. The number and percentage of subjects entering and completing each treatment of the clinical study will be presented, including the number and percentage of subjects dosed, the frequency and percentage of subjects completing the treatment, and the frequency and percentage of subjects completing the study,, subjects withdrawing early, and primary reason for withdrawal will be included the summary table.

Listing of the informed consent will be presented using the randomized population [Listing 16.2.1.2].

Subjects who did not meet the inclusion criteria will be listed [Listing 16.2.1.3], and subjects who did meet the exclusion criteria will be listed [Listing 16.2.1.4].

Subject visits information will be listed using the safety population [Listing 16.2.1.5].

PAREXEL International Statistical Analysis Plan

4.3.6.3 Protocol Deviations

All protocol deviations will be recorded by the Investigator and will be listed by subject and will be discussed between PAREXEL (physician, Data Manager, Biostatistician, PK Scientist/Analyst and Medical Writer) and the Sponsor during the clean file meeting before database lock to determine whether these may warrant exclusion of a subject from the statistical analyses. All protocol deviations will be listed for each subject [Listing 16.2.2].

4.3.6.4 Analysis Population

Classification to analysis populations will be presented in a listing and table [Listing 16.2.3, Table 14.1.2].

4.3.6.5 Demographic and Baseline Data

All demographic and baseline data, including height, weight and BMI, will be presented using the safety population. All demographic and baseline data including height, weight and BMI will be listed [Listing 16.2.4.1]. Descriptive statistics will be obtained for the continuous variables by dose and by ethnicity: age, height, Day -1 weight, and BMI [Tables 14.1.3.1 and 14.1.3.2 respectively]. Frequencies and percentages of subjects will be tabulated for the categorical variables by dose and by ethnicity: gender, race, and ethnicity [Tables 14.1.3.3 and 14.1.3.4 respectively].

All other baseline characteristics, including drug abuse, alcohol abuse, smoking history, caffeine use, other stimulating beverages, and blood or plasma donation will be listed [Listing 16.2.4.2].

Detailed information of tobacco product use will be listed [Listing 16.2.4.3].

Detailed information of alcohol use will be listed [Listing 16.2.4.4].

4.3.6.6 Medical History

All medical history will be coded using MedDRA version 21.1.

General medical history and medication history will be listed by subject [Listing 16.2.4.5], including the disease/procedure, MedDRA System Organ Class (SOC), MedDRA Preferred Term (PT), start date, and stop date (or ongoing if applicable). Only those body systems where a condition or abnormality has been reported will be listed.

PAREXEL International Statistical Analysis Plan

Reproductive history (female only) will be listed [Listing 16.2.4.6].

4.3.6.7 Laboratory Tests at Screening and Check-in

Laboratory tests performed at screening and check-in (serology, drug and alcohol toxicology screen tests) will be listed using the safety population [Listing 16.2.4.7].

Pregnancy test performed at screening and check-in (serum and urine tests) will be listed using female subjects only in the safety population [Listing 16.2.4.8].

4.3.6.8 Prior and Concomitant Medication

Prior and concomitant medication will be listed by subject using the safety population [Listing 16.2.4.9], the listing will include the following information: reported name, preferred term, the route of administration, dose, frequency, start date/time, duration and indication.

Prior and concomitant medications will be coded using the World Health Organization-Drug Dictionary (WHO Drug Version Global September 2018 B3).

4.3.6.9 Exposure to the Investigational Medicinal Product

The administration of the study drug VIS649 or placebo for the safety population will be listed with dose amounts and times [Listing 16.2.5.1]. Study drug compliance will be summarized [Table 14.1.4].

Tetanus/Diphtheria vaccination of subjects in cohort 5 will be listed with dose amounts and Date time [Listing 16.2.5.2].

4.3.7 Pharmacokinetic Concentration and Parameter Analyses

The analysis of the PK data will be based on the PK population.

For cohort 5, if number of either Japanese subjects or non-Japanese subjects is less than 3, cohort 5 won't be included in "by ethnicity" analysis.

Pharmacokinetic Concentrations

Pharmacokinetic VIS649 serum concentration data will be listed by subject, including actual sampling times relative to dosing and the deviation from the scheduled sampling time [Listing 16.2.6.1].

PAREXEL International Statistical Analysis Plan

Concentrations will be summarized by dose and nominal PK sampling time [Table 14.2.1].

Concentrations will be summarized by ethnicity, dose and nominal PK sampling time [Table 14.2.2].

The following descriptive statistics will be used: n, arithmetic mean, geometric mean, SD, coefficients of variation (CV%), geometric CV% [REDACTED] [REDACTED] [REDACTED] [REDACTED]

[REDACTED], minimum, maximum and median. The number of values above the lower limit of quantification (LLOQ) will also be presented.

Handling of values below the limit of quantification (BLQ) in listings and for the calculation of descriptive statistics at each time point:

All concentrations below the limit of quantification (BLQ) or missing data will be labeled as such in the concentration data listings. Missing samples will be reported as no sample ("NS") and excluded from analysis. Values that are BLQ will be substituted with zero for the calculation of descriptive statistics of concentration by time point and will be displayed as "not calculable" or NC for the calculation of statistical summaries.

- Figure 14.2.1.1: Combined Subject Profiles for VIS649 Plasma Concentration Time Data - Linear Scale
- Figure 14.2.1.2: Combined Subject Profiles for VIS649 Plasma Concentration Time Data - Semi-Logarithmic Scale

The actual sampling time will be used on the x-axis. Time on the x-axis will be in days.

- Figure 14.2.1.3: Mean (\pm SD) Plasma VIS649 Concentration Time Data -Linear Scale
- Figure 14.2.1.4: Mean Plasma VIS649 Concentration Time Data - Semi-Logarithmic Scale

The nominal sampling time will be used on the x-axis. All treatments will be overlaid on the same plot. Time on the x-axis will be in days.

To visualize the comparison between ethnicity groups for each treatment the following descriptive pharmacokinetic graphs will be generated. For each figure Japanese and Non-Japanese subjects will be shown on the same plot with separate figures for each level of treatment. Figures will be displayed in black and white.

PAREXEL International Statistical Analysis Plan

- Figure 14.2.1.5: Japanese vs Non-Japanese Mean (\pm SD) Plasma VIS649 Concentration Time Data -Linear Scale
- Figure 14.2.1.6: Japanese vs Non-Japanese Mean Plasma VIS649 Concentration Time Data - Semi-Logarithmic Scale - The nominal sampling time will be used on the x-axis. All treatments will be overlaid on the same plot. Time on the x-axis will be in days

Pharmacokinetic Parameters

Pharmacokinetic parameters will be listed [Listing 16.2.6.2] and summarized by dose [Table 14.2.3] and by ethnicity and dose [Table 14.2.4] separately.

The summaries of PK parameters will use following descriptive statistics: n, arithmetic means, SD, coefficients of variation (CV%), geometric CV% [REDACTED]

[REDACTED], minimum, maximum and median. For t_{max} only median, minimum, and maximum values will be presented. No descriptive statistics will be determined when fewer than three individual PK parameters are available.

No value for $AUC_{0-\infty}$, CL, $t_{1/2}$, or Vd, will be reported for cases with inaccurate estimation of λ_z .

Dose Proportionality Analysis

Due to the complex nature of the association between the systemic exposure and the dose, the assessment of the dose proportionality will not be based solely on a strict statistical rule given the small sample size for each dose level. Rather, several considerations will be taken into account for assessing dose proportionality, such as results derived from the Power Model (e.g., the slope estimate, and the width of the 95% confidence intervals) and qualitative assessment specific to the PK of the drug and clinical relevance.

[REDACTED]

[REDACTED]

[REDACTED]

[REDACTED]

[REDACTED]

[REDACTED]

[REDACTED]

PAREXEL International

Statistical Analysis Plan

Table 14.2.5.1 will summarize the results of the regression analysis.

To assess the linear relationship with the dose of VIS649 administered graphically, scatter plots of serum PK parameters (dose normalized to a 1mg dose) versus dose will be generated for the dose dependent PK parameters C_{max} , AUC_{0-112d} , AUC_{0-last} and AUC_{0-inf} (Figure 14.2.1.7), the figure will include the 90% CI prediction and confidence band.

Ethnicity Effect on PK

RUN;

QUIT;

Visterra Inc.
VIS649-101

Final 1.0
3/Jun/2019

TP-EP.BS-WW-001-05
Effective date: 29 Jul 1

Effective date: 29 Jul 13

Page 43 of 68

PAREXEL International Statistical Analysis Plan

Table 14.2.5.2 will present ANCOVA results for pharmacokinetic parameters by dose and will have least square estimate and 95 % CI for the geometric means for each ethnicity along with the 90% CI for the ratio of geometric means (test=Japanese / reference=non-Japanese).

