1.2 Secondary Objectives

- To characterize the pharmacokinetic (PK) profile of VIS649
- To evaluate the effect of ethnicity on the PK profile of a single intravenously (IV) administered dose of VIS649 in healthy Japanese and non-Japanese subjects
- To characterize the levels of anti-drug antibodies
- To characterize the effect of VIS649 on pharmacodynamic (PD) parameters including:
 - changes in serum total IgA, IgG and IgM concentrations and time to recovery.
 - changes in circulating lymphocyte populations in cohorts 1-4 only (this assessment will be done for all lymphocytes, and also for lymphocyte subsets that are noted to show changes from baseline)

PAREXEL International
Statistical Analysis Plan

- To assess ADA status impact on VIS649 PK parameters

■ [REDACTED]

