3. STUDY DESIGN

3.1 Study Design

This is a phase 1, randomized, placebo-controlled, double-blind, and single ascending dose study to investigate the safety, tolerability, PK/PD of the IV administration of VIS649 in healthy subjects.

The study will be conducted in five sequential dosing cohorts. Cohorts 1-4 will enroll 9 subjects per cohort. Cohorts 1-4 will enroll 4 Japanese subjects and will be randomized to VIS649 or placebo in a ratio of 7:2 (7 active, 2 placebo). The fifth cohort will enroll up to 15 subjects with targeted but non-mandatory enrollment of up to 5 Japanese subjects. The subjects in cohort 5 will be randomized to VIS649 or placebo in a ratio of 10:5 (10 active, 5 placebo). In addition, all subjects in cohort 5 will receive TENIVAC® vaccine.

Sentinel subjects will be utilized in cohorts 1-4 (but not in cohort 5); the first two subjects in each cohort will be randomized to receive either VIS649 (n=1) or placebo (n=1) and will receive study drug at least 24 hours before the remaining subjects in the cohort (7 subjects) are dosed. These 2 subjects shall remain confined to the study center for 24 hours after study drug administration. Cohort 5 does not require sentinel subjects as the dose of VIS649 has already been evaluated in cohort 3.

The Schedule of Assessments is listed in Table 1.

PAREXEL International
Statistical Analysis Plan

Table 1 Schedule of Assessments

Activity	Screen	Base - line	Post-Dosing Period Assessments																Additional Visits ⁷	
			BL D-1	D1	D2	D3	W1/ D7	W2/D 14	W3/D 21	W4/D 28	D31 ⁹	W5/ D35	W6/ D42	W7/ D49 (cohorts 1-4 only)	W8/ D56	W10/ D70	W12/ D84	W14/ D98	W16/ D112	W 20
Time Point (Day)	Days - 28 to -1	BL D-1 pre-dose																		
+/- visit allowance	N/A	N/A	N/A	N/A	+1	+/-1	+/-3	+/-3	+/-3	+/-3	+/-1	+/-3	+/-3	+/-3	+/-3	+/-3	+/-3	+/-3	+/-5	+/-5
In-house Day		x	x	x1																
Ambulatory Visit	x				x	x	x	x	x	x	x	x	x	x	x	x	x	x ²	x ²	
Procedures																				
Informed Consent/HIPAA	x																			
Verify Inclusion/exclusion criteria	x	x																		
Demographics & Medical History	x																			
Pregnancy Test (Serum β-hCG)	x																		x	
Pregnancy Test (urine dip stick)		x																		
Serology - HBsAG, Hepatitis C, HIV-test	x																			
Drug & alcohol toxicology screen	x	x																		
Physical Examination - Full	x	x																		
Physical					x				x						x		x		x	

PAREXEL International
Statistical Analysis Plan

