3.4 Randomization

Randomization and blinding will occur according to a core randomization list administered by the site's unblinded pharmacist.

PAREXEL International
Statistical Analysis Plan

Prior to dosing on Day 1, all screened and eligible subjects will be assigned a randomization number in accordance with the randomization code generated by PAREXEL International. If subjects are withdrawn prematurely from the study and are replaced under the direction of the Sponsor, then a replacement randomization number will be assigned. Cohort, randomization numbers and replacement numbers are listed in Table 3.

Table 3 Randomization Numbers and Treatment Assignment

Dose Group	Randomization Numbers	Replacement Numbers	Treatment Assignment	
Cohort 1	[REDACTED]	[REDACTED]	0.5 mg/kg VIS649 (N=7)	Placebo (N=2)
Cohort 2	[REDACTED]	[REDACTED]	2.0 mg/kg VIS649 (N=7)	Placebo (N=2)
Cohort 3	[REDACTED]	[REDACTED]	6.0 mg/kg VIS649 (N=7)	Placebo (N=2)
Cohort 4	[REDACTED]	[REDACTED]	12 mg/kg VIS649 (N=7)	Placebo (N=2)
Cohort 5	[REDACTED]	[REDACTED]	VIS649 6.0 mg/kg plus vaccine (N=10)	Placebo plus vaccine (N=5)

No more than one Japanese subject per cohort may be randomized to receive placebo in cohorts 1-4. No more than two Japanese subjects may be randomized to receive placebo in cohort 5.

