4.3.2 Statistical Significance Level

All statistical tests will be performed at the 5% level of significance and confidence intervals (CI) will be two-sided at the stated coverage probability.

PAREXEL International

Statistical Analysis Plan

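### The visible specification for the ethnicity effect on PK gives ratios by dose and describes no overall dose-adjusted ratio; if none is produced, the cohort 1–4 intervals are about 2.0 to 2.35 times as wide as one pooled interval.

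*SAP*

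**What the plan says.** SAP 1.2 states the objective as one question, not one per dose: "To evaluate the effect of ethnicity on the PK profile of a single intravenously (IV) administered dose of VIS649". Protocol 2.2 has the same objective, worded as race.

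The output that answers it is described at the end of SAP 4.3.7: "Table 14.2.5.2 will present ANCOVA results for pharmacokinetic parameters by dose". The table is to hold least-squares geometric means with 95% CIs for each ethnicity, "along with the 90% CI for the ratio of geometric means (test=Japanese / reference=non-Japanese"). The text under the sub-heading on the ethnicity effect is missing from the public copy, apart from the closing statements of a SAS procedure. It cannot be read whether dose is a model factor, a covariate or a BY variable, or whether an overall contrast is requested.

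Group sizes come from SAP 3.1, "Cohorts 1-4 will enroll 4 Japanese subjects and will be randomized to VIS649 or placebo in a ratio of 7:2", and SAP 3.4, "No more than one Japanese subject per cohort may be randomized to receive placebo in cohorts 1-4". Cohort 5 (10 active, 5 placebo) has up to 5 Japanese subjects, not mandatory, and receives the cohort 3 dose of 6.0 mg/kg. Under SAP 4.3.7 it drops out of the by-ethnicity analysis if either ethnicity has fewer than 3 subjects.

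Neither the list of tables in SAP section 6 nor Protocol 8.8 mentions an overall ratio. Protocol 8.8 plans only descriptive PK summaries by cohort for the two groups.

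**The concern.** Read literally, the table gives four or five separate Japanese/non-Japanese ratios per PK parameter, each from a handful of subjects, for an objective that asks one question. Such intervals would be too wide to say much about an ethnicity effect.

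They also invite chance findings. With four independent 90% CIs and no true effect, the probability that at least one excludes 1 is 1 − 0.9⁴ = 0.34 per parameter. If no main result is named in advance, the report can stress whichever dose looks most or least different.

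The sample size had no formal basis (SAP 3.3), so the precision available for this objective depends on how the analysis uses the data already planned.

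**Working it through.** The documents give no precision target and no between-subject CV for this comparison, so there is no figure of the plan's own to reproduce. The check compares 90% CI widths.

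**Inputs**
- Active subjects per cohort, cohorts 1–4: 7. Four Japanese subjects are enrolled and at most one is on placebo, so the split is 3 v 4 or 4 v 3 (SAP 3.1, 3.4).
- Active subjects over cohorts 1–4: 28.
- CI: two-sided 90% (SAP 4.3.7, 4.3.2).
- s: between-subject SD of the log parameter, taken as equal across doses and groups. All active subjects are assumed to contribute.

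**Formulas.** Log-scale half-width = t(0.95, df) × SE.
- One dose: SE = s√(1/3 + 1/4) = 0.764s.
- One dose-adjusted ratio: SE = s/√Σ[nJ·nN/(nJ + nN)]. Each cohort gives 12/7 = 1.714 and four give 6.857, so SE = 0.382s.

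**Cohorts 1–4**

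| Analysis | df | Half-width | Relative to dose-adjusted |
|---|---|---|---|
| By dose, separate models | 7 − 2 = 5 | 2.015 × 0.764s = 1.539s | 2.35 |
| By dose, one dose-by-ethnicity model with pooled error | 28 − 8 = 20 | 1.725 × 0.764s = 1.317s | 2.01 |
| One dose-adjusted ratio | 28 − 5 = 23 | 1.714 × 0.382s = 0.654s | 1 |

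These log-scale factors do not depend on the CV. Pooling the error gains degrees of freedom, but a ratio that is free to differ by dose still rests on that dose's subjects.

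**With cohort 5, merged with cohort 3 as one 6 mg/kg level.** There are 38 active subjects in all and 17 at 6 mg/kg, split from 6 v 11 to 9 v 8 if cohort 5 has 3 to 5 Japanese subjects on active drug.
- 6 v 11: Σ = 3 × 12/7 + 66/17 = 9.025. The pooled half-width is 1.692 × 0.333s = 0.563s (df 33). At 6 mg/kg, SE = 0.508s, so the half-width is 0.890s (df 15, separate) or 0.861s (df 30, pooled error). Factors: 1.58 and 1.53.
- 9 v 8: Σ = 3 × 12/7 + 72/17 = 9.378. The pooled half-width is 0.553s. At 6 mg/kg it is 0.852s or 0.825s. Factors: 1.54 and 1.49.
- At the other three doses the factors are 2.73–2.78 (separate) and 2.30–2.35 (pooled error).

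If cohort 5 is kept as its own group, its factor is 2.12–2.27 (separate) or 1.94–2.07 (pooled error).

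**Illustration: 90% limits around a ratio of 1, cohorts 1–4.** The CVs are assumed, and s = √ln(1 + CV²).

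| CV | By dose, separate | By dose, pooled error | Dose-adjusted |
|---|---|---|---|
| 20% | 0.74–1.36 | 0.77–1.30 | 0.88–1.14 |
| 30% | 0.64–1.57 | 0.68–1.47 | 0.83–1.21 |
| 40% | 0.55–1.81 | 0.60–1.66 | 0.78–1.29 |

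**The case against.** The strongest objection is the redaction. The words on dose in the table description are the only positive support for a dose-by-dose analysis, and other visible features point the other way. The same sentence speaks of geometric means for each ethnicity and of a single ratio. The title of Table 14.2.5.2 in SAP section 6 has no by-treatment qualifier, whereas Tables 14.2.2 and 14.2.4 do. An ANCOVA has a covariate, and dose is one candidate. A reader might infer that the SAP has chosen by-dose ratios instead of a dose-adjusted one. The documents do not support that as fact, because what is blacked out cannot be counted as absent. This part of the objection stands.

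A reader might also infer that the by-dose intervals are at least twice as wide at every dose. That fails at 6 mg/kg if cohort 5 qualifies and is merged with cohort 3. Even in cohorts 1–4 the pooled-error factor clears two only narrowly.

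Third, by-dose ratios have a use. A common ratio across doses is an assumption. SAP 4.3.7 calls the exposure–dose relation complex, and Protocol 5.2 treats zero nonlinearity as a conservative assumption made for its safety-margin simulations. This is a reason to keep the by-dose rows, not a reason to have no overall row.

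Finally, no visible decision rule or precision target depends on this ratio, so no stated criterion is breached. That limits the weight of the point but does not remove the gain in precision.

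**Conclusion.** The point holds conditionally. The visible specification gives the ethnicity ratios by dose and describes no overall one; whether the redacted model supplies one is unknown. If only by-dose ratios are reported, the 90% CIs in cohorts 1–4 are 2.01 to 2.35 times as wide on the log scale as one dose-adjusted CI from the same 28 subjects. With cohort 5 merged at 6 mg/kg, the factor is about 1.5–1.6 there and about 2.3–2.8 elsewhere.

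These factors assume equal log-scale variance, a common ethnicity ratio across doses, and a contribution from every active subject. The absolute limits rest on assumed CVs. This is an inexpensive improvement and clarification, not a demonstrated error in the analysis.

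**What to change.** In SAP 4.3.7, make the main row of Table 14.2.5.2 one Japanese/non-Japanese geometric mean ratio with 90% CI for each PK parameter. Estimate it from a model of the log parameter with dose group and ethnicity as factors, over all cohorts eligible for the by-ethnicity analysis. State whether cohorts 3 and 5 count as one dose group. Keep the by-dose ratios as supportive rows and as a check that the ratio is similar across doses. If the redacted model already gives the overall ratio, correct the table description instead.

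The cost is one model statement and one table row, with no new data or procedures. The downside is the assumption of a similar ethnicity effect across doses. With 3 v 4 subjects at most doses, the by-dose rows can expose only a large departure from it.
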